#### 5.8.4 Return or Destruction of Study Drug

At the completion of the study, there will be a final reconciliation of drug shipped, drug dispensed, drug returns, and drug remaining. This reconciliation will be logged on the drug reconciliation form, signed and dated. Any discrepancies noted will be documented and investigated, prior to return or destruction of unused study drug. Drug destroyed on site will be documented in the study files.

### 6 Study Procedures

#### 6.1 Visit 1 (day 0)

At the time of the initial assessment (Randomization visit, day 0 on the flow chart), the complete history and physical examination performed by the health care provider attending the patient will be recorded by the enrolling study personnel. Recent baseline laboratory data (collected within 4 weeks) will include complete blood counts (CBC), creatinine, and ALT (or AST). The creatinine clearance will be calculated using the method of Cockcroft and Gault:

Cockcroft-Gault GFR =  $(140\text{-age}) * (\text{Wt in kg}) * (0.85 \text{ if female}) / (72 * \text{Cr})$   
These laboratory values must be current within 4 weeks of this initial encounter.

#### 6.2 Surveillance and Follow up.

Following randomization, subjects will be assigned to either active treatment with apixaban or placebo control for a total of 90 days. Each subject will then undergo follow up ultrasound imaging at 7 days (+/- 2 days), 14 days (+/- 2 days) and 90 days (+/- 7 days). This ultrasound imaging study will focus on venous thrombus propagation into the proximal venous segments. At each follow up, all venous segments of the involved lower extremity will be imaged. This imaging should be performed at a site participating in this research project. Patients will be called at Days 30 & 60 (+/- 7 days) to check their health status, adverse reactions and medication compliance.

Patients will be instructed to report to the clinic immediately if they had any bleeding or symptoms of recurrent deep-vein thrombosis, pulmonary embolism, or both. All suspected episodes of recurrent thrombosis will be investigated with the use of objective tests, according to prespecified diagnostic algorithms. At 3 months (+/- 7 days), patients will return for a routine clinically indicated ultrasound and clinical assessment.

Study Activity	Day 0	Day 7 (± 2 days)	Day 14 (± 2 days)	Day 30 (± 7 days)	Day 60 (± 7 days)	Day 90 (± 7 days)
Informed consent	X					
History	X					
Concurrent meds	X	X	X	X	X	X

Collect data from clinical physical exam (Ht, Wt, BSA, VS)	X					
Collect Lab Values (CBC, creatinine, ALT/AST) a	X a					
Adverse event evaluation		X	X	X	X	X
B-HCG	X b					
Drug dispensing and collection of any unused drug	X					X
Ultrasound c	X	X	X			X
Telephone survey (appendix A)				X	X	

a = Collect data from clinical testing in the last 4 weeks.

b = Women of child bearing potential only. If not done clinically in the last 2 weeks.

c = The baseline ultrasound will be requested and performed by the provider caring for the patient. This will be a clinically indicated study and will not be repeated for study purposes. This US will serve as the baseline imaging study for trial purposes.

## 7 Statistical Considerations

### 7.1 Sample Size Determination

An anticipated venous thromboembolic event rate of 12.6% within 3 months for patients randomized to standard medical observation and placebo is expected (Table Below). The composite venous thrombosis event rate of 12.6% includes a thrombus propagation rate of 5.4%, pulmonary embolism rate of 0.5% and recurrent venous thrombosis rate of 6.7% over this time interval. Specifically, for sample size calculations, we consider an **event rate of 10% for the placebo arm**. By comparison, thromboembolic outcomes in the AMPLIFY trial for those subjects randomized to apixaban was 2.3% at 6 months. We hypothesize the apixaban arm in this study will result in a 3 month event rate in the range of 1.0% to 2.3%. Specifically, for sample size calculations, we consider an **event rate of 1.6% for the apixaban arm**.

Trial	n	Population	Treatment	Follow up Duration	Propagation	PE	VTE Recurrence	Major Bleed
Hull 	32	All comers	Warfarin UFH 5000 BID	3 mo		0 0	0 0	
Lagerstedt 	51	Inpatient	Warfarin Placebo	3 mo		0 3.6%	0 29%	8.7% 0
Ferrara 	192	Post op	LMWH/Warf Single vein  multiple vein	6 wk 3 mo	14% 9%	0 0		0 0
Schwarz 	107	All comers	LMWH x 10d Placebo	3 mo	3.8% 3.8%	0 0		0 0
Horner 	70	All comers	LMH/Warf NSAIDs	3 mo	0 8.6%	0 2.9%		0 0
Righini 	259	All comers	LMH x 42d Placebo	3 mo	1.6% 5.3%	1.6% 0	0 4%	0.8% 0

The detailed listing of assumptions used to estimate the sample size are as follows:

- 3 month thromboembolic outcomes for the placebo arm = 10.0%
- 3 month thromboembolic outcomes for the apixaban arm = 1.6%
- Equal allocation to both treatment groups

- One interim analysis using O'Brien-Flemming-like alpha spending function conducted after 40% of the enrolled participants have their 90 day outcome assessed (40% information fraction)
- An overall two-sided significance level of 0.05 with a final adjusted alpha of 0.0492 (after interim analysis correction)
- Target power = 80%
- Normal approximation to the proportions, two independent groups, no continuity correction

Based on the assumptions above, a sample size of 121 per arm would be required. We round this estimate to 125/group (250 total) to account for minor attrition to the intention to treat analysis set including subject dropout and missing data.

## 7.2 Statistical Methods

### 7.2.1 Primary Hypothesis:

We hypothesize that apixaban 5 mg twice daily is associated with a significantly lower rate of the primary composite efficacy outcome compared to matched placebo in patients with calf DVT.

**7.2.1.2 Primary Efficacy Analysis:** All patients randomized to receive at least one dose of apixaban 5 mg or matching placebo control will be included in the primary analysis under intention to treat (see analysis sets below). The analysis of the primary composite endpoint will only include events occurring during the 3 months of study medication use.

Frequency of the primary composite efficacy endpoint will be tabulated by treatment arm without regard to the time the event was observed within the 3 month study period. The Cochran-Mantel-Haenszel test will be used to compare the event rates by treatment group. The pooled estimate of the odds ratio will be used as the primary measure of association for the study.

An exploratory analysis will investigate the time to event is defined as the time from randomization to the first occurrence of a primary composite efficacy outcome event. Patients who were lost to follow-up or who withdrew consent before the end of the three month treatment period will be censored at the last day the patient had a complete assessment for study outcomes within the 3 month study period. The incidence curves of VTE events will be plotted using the Kaplan-Meier estimator by treatment group. The difference in the incidences of the primary composite outcome at 3 months between treatment arms will be estimated and tested using a normal approximation of the binomial distribution.

**7.2.1.3 Safety Analysis:** All patients who received at least one dose of study medication will be included in the safety analysis. The analysis of major bleeding and clinically relevant non-major bleeding events will include those events which occurred during the 3 month study period. Major bleeding events observed later will be described separately.

Frequency of major bleeding and clinically relevant non-major bleeding will be tabulated by treatment arm. The incidence of major bleeding and clinically relevant non-major bleeding will be summarized as a combined endpoint and separate endpoints by treatment arm. The difference in the incidences of the combined endpoint at 3 months between treatment arms will be estimated and tested using a normal approximation of the binomial distribution.

The outcome of net clinical benefit or harm will be assessed as the composite of the primary efficacy outcome or the principal safety outcome up to day 90. The difference in the incidences of the combined endpoint at 3 months between treatment arms will be estimated and tested using a normal approximation of the binomial distribution. All tests will be conducted at the two-sided 0.05 significance level.

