## Study Summary

Title	A Phase IV, Randomized, Double Blind Placebo controlled Study Evaluating the Safety and Efficacy of Apixaban in Subjects with Isolated Calf Vein Thrombosis
Running Title	Golden Calf Trial
Protocol Number	17-009022
Phase	Phase IV
Methodology	Single center, multi-Mayo site randomized, double blind, placebo-controlled, superiority clinical trial.
Overall Study Duration	36 months
Subject Participation Duration	Each individual will be in the study for 3 months
Single or Multi-Site	Single center, multi-Mayo site Trial
Objectives	There are two primary objectives. The first primary objective is to evaluate whether a strategy of active anticoagulation with apixaban is more efficacious than no anticoagulation (i.e., placebo) when monitored with serial ultrasound imaging in the management of patients with isolated calf vein thrombosis (DVT) for the composite endpoint consisting of prevention of thrombus propagation, pulmonary embolism, recurrent venous thromboembolic events, and all cause mortality. The second primary objective, safety, is to assess the combination of major and clinically relevant non-major bleeding for subjects randomized to apixaban vs. placebo control.
Number of Subjects	The number of patients needed is 250, or 125 in each of the two treatment arms.
Diagnosis and Main Inclusion Criteria	Patients will be recruited for study participation if they have a newly diagnosed venous thrombotic event (DVT) limited to the calf veins.
Study Product, Dose, Route, Regimen	Apixaban (10 mg twice daily for 7 days followed by 5 mg twice daily for 3 months) or matching placebo.
Duration of Administration	Total duration of drug administration will be for the duration of study participation 3 months.
Reference therapy	Serial clinical monitoring as is standard of practice with matching placebo. All patients will undergo serial ultrasound imaging at day 7, day 14, and day 90.
Primary Endpoint	Combined endpoint including thrombus propagation, pulmonary embolism, recurrent venous thromboembolism, and all cause mortality over three months.

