### 3.2 Primary Study Endpoints

The primary composite efficacy endpoint of this study will include thrombus propagation either within the calf veins or into proximal deep veins (popliteal, femoral or iliac veins), symptomatic or incidental VTE recurrence or all-cause mortality by day 90. The following criteria will be used to confirm and categorize an outcome VTE event:

1. **Thrombus propagation:** The original calf DVT must be confirmed by either duplex ultrasonography, venography, CT, or MRI. All patients will then undergo serial ultrasound imaging at 7 days, 14 days and 90 days. Propagation is defined by two criteria: (1) when a thrombus previously confined to the calf veins is found to extend into a proximal vein including popliteal, femoral or iliac veins of the ipsilateral limb or (2) if the thrombus extends but remains confined to the calf veins. The thrombus propagation must be confirmed by comparing the new imaging with previous imaging clearly showing extension into a proximal vein not seen on the original imaging study. Thrombus propagation that remains confined to the calf veins must extend beyond 5 cm of the previous thrombus length, extend into a new venous segment (upper, mid, or lower), or involve a new vein (not previously involved) within the calf (example, the original involvement was

confined to the posterior tibial vein and now there is new involvement of the gastrocnemius vein.)

2. **Recurrent DVT:** A recurrent DVT must be distinguished from the original thrombus by comparing serial imaging modalities. In order to be classified as a recurrent event, there must be new filling defects evident on the second study not appreciated on the original images or an interval study clearly showing thrombus resolution.
3. **PE:** Symptomatic pulmonary emboli must be confirmed by either CT, MR or conventional pulmonary angiography or VQ perfusion imaging.
4. **Incidental VTE recurrence:** It is anticipated that recurrent venous thrombosis or thrombus propagation may be identified incidentally (without new or changing symptoms). In order to be classified as an event, the thrombus in question must be confirmed by cross sectional imaging (duplex ultrasonography, venography, CT, MRI or VQ).
5. **All-cause mortality**

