#### **4.4.3 Data Collection and Follow-up for Withdrawn Subjects**

For subjects withdrawn from the study, follow-up data will be collected throughout the protocol defined follow-up period. This is regardless of compliance or tolerance with study medication, provided participants are willing to provide follow up examinations. This data is important to the integrity of the final study analysis since early withdrawal could be related to the safety profile of apixaban. If a subject withdraws consent to participate in the study, for subject safety reasons, attempts will be made to obtain permission to collect follow up information, whenever possible.

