#### **5.2 Treatment Regimen**

Patients randomized to apixaban will be treated with 10 mg twice daily for 7 days followed by 5 mg twice daily for 3 months. Patients assigned to matching placebo will take their tablets in a similar fashion.

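### Section 7.2.1.2 words the primary event window as time on drug inside an intention-to-treat analysis, and the safety set and recurrence definition are each stated two ways

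*Combined protocol and SAP*

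**What the plan says.** **Event window.** Section 7.2.1.2 says that patients "will be included in the primary analysis under intention to treat (see analysis sets below"), and the next sentence reads "The analysis of the primary composite endpoint will only include events occurring during the 3 months of study medication use". The following paragraph tabulates events "without regard to the time the event was observed within the 3 month study period". Section 3.2 defines the endpoint with no drug condition: "symptomatic or incidental VTE recurrence or all-cause mortality by day 90". Section 4.4.3 continues follow-up after withdrawal: "This is regardless of compliance or tolerance with study medication", adding that "This data is important to the integrity of the final study analysis".

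**Length of treatment.** The Study Summary equates treatment with participation: "Total duration of drug administration will be for the duration of study participation 3 months". Section 5.2 says apixaban patients "will be treated with 10 mg twice daily for 7 days followed by 5 mg twice daily for 3 months", whereas 6.2 gives 90 days in total.

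**Analysis sets.** Section 7.2.1.3 restricts the safety analysis to patients who took at least one dose. Section 7.3 puts all randomised patients in both the efficacy and the safety analyses. Section 7.2.1.2 also attaches a one-dose condition to the efficacy population, but refers the reader to 7.3, which includes patients who never took drug.

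**Recurrence.** Section 3.1 lists symptomatic recurrence only. Section 3.2 counts incidental recurrence as its own category, and 4.4.1 treats asymptomatic recurrence as a thrombotic endpoint.

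**The concern.** A rule that counts only events during drug use is an on-drug rule, and it sits in an analysis called intention to treat. Sections 4.4.1 and 4.4.2 let patients stop or interrupt study drug for bleeding, non-adherence, laboratory values or their own choice. If such a patient then has a first VTE or dies before day 90, the literal sentence drops the event while 3.2 counts it. That would weaken the randomised comparison and discard data that 4.4.3 describes as needed. With few events expected, leaving the window open also allows the reading to be chosen once results are known.

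The gap is limited to patients who stop or interrupt before any efficacy event. A first thrombotic event that itself leads to stopping drug has already been counted.

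The safety-set conflict touches the second primary objective, and the recurrence conflict touches the definition of the primary endpoint.

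**Working it through.** **1. The passages on the window, side by side.**

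- For the nominal three months: 3.2 (day 90); the second paragraph of 7.2.1.2 (study period); the exploratory time-to-event rule in 7.2.1.2, which censors for loss to follow-up or withdrawn consent but not for stopping drug; the net-benefit definition (day 90); the interim analysis (90-day outcome); and 7.3, which names an on-treatment analysis apart from the primary one.
- For the on-drug reading: the single sentence in 7.2.1.2, whose word *only* makes it an exclusion rule. The safety paragraph (7.2.1.3) defines its window by the study period instead, so the two phrases could be taken as deliberately different.

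**2. Reproduce the plan's sample size.** Inputs from 7.1: p0 = 0.10, p1 = 0.016, two-sided alpha 0.0492, power 80%, normal approximation, no continuity correction. With mean rate p̄ = 0.058:

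n = [1.967·√(2·0.058·0.942) + 0.842·√(0.10·0.90 + 0.016·0.984)]² / 0.084²
= [1.967·0.3306 + 0.842·0.3252]² / 0.007056 ≈ 121 per arm, as stated.

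Power at 125 per arm = Φ[(0.084·√125 − 1.967·0.3306)/0.3252] = Φ(0.889) = 81.3%.

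**3. Expected events.** 125 × 0.10 = 12.5 on placebo and 125 × 0.016 = 2.0 on apixaban, 14.5 in all.

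**4. Illustration of uncounted events.** The documents give no stopping rate, so the share is assumed. Both rates are multiplied by (1 − share) and the power formula is repeated at 125 per arm.

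| Share uncounted, both arms | Events lost of 14.5 | Rates compared | Power |
|---|---|---|---|
| 0% | 0 | 10.0% vs 1.60% | 81.3% |
| 5% | 0.7 | 9.5% vs 1.52% | 79.1% |
| 10% | 1.5 | 9.0% vs 1.44% | 76.8% |
| 15% | 2.2 | 8.5% vs 1.36% | 74.2% |
| 20% | 2.9 | 8.0% vs 1.28% | 71.4% |

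**5. Unequal loss.** Counts follow Binomial(125, 0.10) and Binomial(125, 0.016), each event is dropped independently, and an unstratified pooled z-test at 0.0492 is applied before and after.

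- 20% of apixaban and 5% of placebo events uncounted: 3.3% of trials gain significance and 1.9% lose it.
- 5% of apixaban and 20% of placebo events uncounted: 0.3% gain and 15.7% lose.

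The planned odds ratio is (0.016/0.984)/(0.10/0.90) = 0.146. Dropping 30% of apixaban events only gives (0.0112/0.9888)/(0.10/0.90) = 0.102. Dropping 30% of placebo events only gives (0.016/0.984)/(0.07/0.93) = 0.216.

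**6. Results near the expected counts are not fragile.** For 2 vs 12 events, z = 0.08/√(2·0.056·0.944/125) = 2.75, p = 0.006.

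**7. The other two conflicts** need no arithmetic. Asymptomatic propagation counts under both 3.1 and 3.2, so only incidental recurrence that is not propagation is affected. The documents give no share of recurrence expected to be incidental, so I put no figure on it.

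**The case against.** The strongest reply is that this is one loose sentence whose meaning is clear from its surroundings. It speaks of a fixed three months, the Study Summary treats drug administration and participation as the same period, and a plan that meant to drop off-drug events would be expected to censor at drug stop. I accept this as the likely intent. A reader might infer from the sentence that the trial plans an on-treatment primary analysis; the documents do not support that.

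The reply does not make the sentence safe. It never says that off-drug events count. The on-treatment set in 7.3 is defined by having taken one dose, not by an event window, so it does not settle which events are counted.

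It is also fair to say that the side issues are small in practice. Sections 5.4 and 5.5 start drug on the day of evaluation, so never-dosed patients should be few. Section 3.2 is the detailed endpoint definition, and the follow-up form in Appendix B2 separates symptomatic from incidental recurrence, so either version can be derived. These points limit the effect but leave the contradictions in place.

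A reader might also try to derive further window ends from the 200-tablet bottle. A supply count is not an analysis window, and 3.2 sets the endpoint at day 90.

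**Conclusion.** The point holds as a defect of wording that should be corrected before unblinding. The primary event rule, read literally, contradicts 3.2 and 4.4.3; the safety set and the recurrence component are each stated in two incompatible ways.

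The likely effect is small. The power range of 79.1% to 71.4%, against 81.3%, rests on assumed equal losses of 5% to 20% and on the literal reading being applied; neither can be established from the documents. The power and switch figures use an unstratified test as an approximation to the planned Cochran-Mantel-Haenszel test.

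A reader might infer that the rule favours apixaban, or that it costs only power and cannot create a false positive. Neither follows: unequal loss moves the result either way, and no direction of bias is claimed.

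Two related gaps belong with this point. A final scan on days 91 to 97 complies with 6.2 but falls after the day-90 close in 3.2, with no rule for it. The treatment lengths in 5.2 and 6.2 also do not agree.

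**What to change.** Replace the event sentence in 7.2.1.2 with:

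> The primary analysis includes all randomised participants as allocated (subject to the consent and IRB exception in 7.3) and counts every adjudicated component event from randomisation through day 90, whether or not study drug was still being taken; propagation or recurrence found on the protocol day-90 scan (days 83–97) counts.

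Then:

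- delete the one-dose condition from the primary population in 7.2.1.2;
- state one safety set, the same in 7.2.1.3 and 7.3;
- align 3.1 with 3.2 on incidental recurrence;
- apply the same window, including the scan rule, to net clinical benefit;
- if wanted, keep an on-drug event count as a labelled sensitivity analysis.

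The sponsor must reconcile the treatment-length statements in 5.2 and 6.2; no view is taken here on which is right.

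The cost is a wording amendment before unblinding. The sample size does not change, and no visit or patient contact is added: follow-up after stopping drug is already collected under 4.4.3, and the scan window is already in 6.2.

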## 2. Hemorrhagic endpoint:

- a. Non-major Clinically Relevant Bleed:** If the patient suffers a non-major clinically relevant bleed, then the study medication should be temporarily discontinued until the site and circumstances of the bleeding event have been evaluated. If these circumstances can be rectified, then the patient can remain on the study medication which will be restarted as soon as clinically indicated.
- b. Major Bleed:** If the patient suffers a major bleed, then the study medication should be discontinued and the patient cared for as clinically appropriate. Under these circumstances, the patient will be unblinded to determine the specific study medication (apixaban or matching placebo) by contacting the Central Office (see page 1 of protocol). During emergency circumstances where patient safety is felt to be compromised, study allocation can be rapidly determined by drawing a heparin antiXa activity measure. If the patient is allocated to apixaban, the level will be elevated, unless they are not taking their medication. For patients allocated to placebo the levels will be undetectable. The unblinding site must notify the central office of the unblinding event within 72 hours of becoming aware. Whether to restart an alternative anticoagulant will be left at the discretion of the medical care provider attending the patient.
- c. Life-threatening Bleed:** If the patient suffers a life-threatening bleed, then the study medication should be discontinued and the patient cared for as clinically appropriate. During emergency circumstances where patient safety is felt to be compromised, study allocation can be rapidly determined by drawing a heparin antiXa activity measure. If the patient is allocated to apixaban, the level will be elevated, unless they are not taking their medication. For patients allocated to placebo the levels will be undetectable. The unblinding site must notify the central office of the unblinding event within 72 hours of becoming aware. During normal business hours, the patient may be unblinded by contacting the Central Office (see page 1 of protocol). Treatment may include the use of prothrombin complex concentrates (K-Centra) depending on which study medication the subject was receiving (apixaban or placebo). Once the specific antidote for direct oral factor Xa inhibitors, andexanet alpha, has been FDA approved, the use of this medicine would also be appropriate.

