## **7.3 Subject Population(s) for Analysis**

The subject populations whose data will be subjected to the study analysis both for the primary efficacy and safety analyses will include all randomized population under the intention to treat principle. Any subject randomized into the study, regardless of whether they received study drug will be included in the primary efficacy analysis provided the participant does not withdraw consent for use of any data collected in the course of the study or as otherwise required by institutional review board determination.

The per protocol analysis set will also be utilized for exploratory analyses. For this analysis, the participant will be expected to have obtained all outcome measurements over the 90 days along with >80% compliance with medication. Furthermore, the participant will need to not have a three day period (6 half-lives of apixaban) with no study medication. We will also perform a “full analysis set” and an “on-treatment” analysis for the study outcomes. For the purpose of this study, the full analysis set will be determined in accordance with ICH E9 guidelines. The on-treatment analysis data set will include subjects who are randomized to study and take at least one dose of study medication.

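### Section 7.2.1.2 limits primary events to the period of study medication use, which contradicts the intention-to-treat analysis and the follow-up after drug stop that the plan sets out elsewhere

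*Combined protocol and SAP*

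**What the plan says.** The first paragraph of 7.2.1.2 describes the primary efficacy analysis as intention to treat. It then sets the event window: "The analysis of the primary composite endpoint will only include events occurring during the 3 months of study medication use".

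Other parts of the plan set a different window or presuppose one:

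- The next paragraph of 7.2.1.2 tabulates the endpoint "without regard to the time the event was observed within the 3 month study period".
- The safety analysis in 7.2.1.3 "will include those events which occurred during the 3 month study period".
- Section 3.2 defines the endpoint by a fixed date: "symptomatic or incidental VTE recurrence or all-cause mortality by day 90".
- Section 7.3 on the population: "Any subject randomized into the study, regardless of whether they received study drug will be included in the primary efficacy analysis". It also lists a separate on-treatment analysis.
- Section 4.4.3 continues follow-up of withdrawn subjects to the end of the protocol period and adds: "This is regardless of compliance or tolerance with study medication".
- Section 4.4.1 gives a route to early drug stop that is not a primary efficacy event: "If the patient suffers a major bleed, then the study medication should be discontinued and the patient cared for as clinically appropriate". Section 4.4.2 lists others: low platelets, renal or hepatic impairment, and non-adherence.

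Section 6.2 allows the last scan 7 days either side of day 90, so as late as day 97.

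**The concern.** A window tied to drug use and a population defined by randomization do not fit together. If both are applied as written, a subject who stops drug at day 30 after a bleed counts as a full subject at risk for 90 days but can contribute an event for only 30 of them. A never-dosed subject, whom 7.3 includes, can contribute none. The loss also reaches the mortality component: a death after a bleed that had already ended study drug would fall outside the window.

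Events leave the numerator while the denominator stays the same, so the arm that stops drug more often is favoured. Section 4.4.3 itself recognises that early withdrawal may be related to the safety of apixaban, so unequal stopping cannot be ruled out. The plan expects about 14.5 primary events (125 × 0.10 + 125 × 0.016 = 12.5 + 2.0), so a single event carries weight.

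There is also a practical risk. Two analysts following 7.2.1.2 could count different primary events, and settling the matter after unblinding would be open to criticism.

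**Working it through.** **1. The plan's own figure.** Inputs from 7.1: placebo 10%, apixaban 1.6%, two-sided alpha 0.0492, power 80%, equal arms, normal approximation without continuity correction.

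n = [z(α/2)·√(2p̄(1−p̄)) + z(β)·√(p₁(1−p₁) + p₂(1−p₂))]² / (p₁−p₂)², with p̄ = 0.058, z(α/2) = 1.967, z(β) = 0.842.

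n = [1.967 × 0.3306 + 0.842 × 0.3252]² / 0.084² = 120.96, so 121 per arm, as stated. Power at 125 per arm is 81.3%.

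**2. The windows compared.**

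| Place | Window |
|---|---|
| 7.2.1.2, first paragraph | 3 months of study medication use, events outside it excluded |
| 7.2.1.2, second paragraph | 3-month study period |
| 7.2.1.3, bleeding | 3-month study period |
| 3.2, endpoint definition | by day 90 |
| 4.4.3, data collection | protocol follow-up period, regardless of compliance |

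Only the first row ties counting to drug use. Stops after a thrombotic event do no harm, because the first event has already been counted. The affected subjects are those who stop for another reason and those never dosed.

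**3. Events that could go uncounted on apixaban.** Assumptions, none of them in the documents: a share d stop halfway through and then carry the placebo risk for the remaining half, 0.5 × 0.10 = 0.05.

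Uncounted apixaban events = 125 × d × 0.05:
- d = 1%: 0.06
- d = 4%: 0.25
- d = 8%: 0.5

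The figure reaches one event only at d = 16% (125 × 0.16 × 0.05 = 1.0).

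**4. Literal counting against counting all events, 125 per arm.** Same assumptions, with the same share stopping in both arms and placebo stoppers keeping a 10% risk.

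- All events: placebo 10%; apixaban 0.016 × (1 − d/2) + 0.10 × d/2.
- Literal: both planned rates multiplied by (1 − d/2).

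| Stop share d | Apixaban rate, all events | Odds ratio, all events | Power, all events | Odds ratio, literal | Power, literal |
|---|---|---|---|---|---|
| 5% | 1.81% | 0.166 | 78.6% | 0.147 | 80.2% |
| 10% | 2.02% | 0.186 | 75.7% | 0.147 | 79.1% |
| 20% | 2.44% | 0.225 | 69.6% | 0.148 | 76.8% |

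Literal counting keeps the odds ratio near its planned 0.146 whatever the stopping rate. Counting all events shows the dilution that intention to treat is meant to show.

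**5. The Day 90 scan.** Nothing states how a clot first seen on days 91 to 97 is counted. Suppose scans are spread evenly over the 15 allowed days, so that 7/15 fall after day 90, and that a strict day-90 cut is applied. If 10%, 25% or 50% of events are first seen on that scan, the loss in both arms is 4.7%, 11.7% or 23.3% (share × 7/15), and power is 79.3%, 75.9% or 69.5%. At the 12.6% placebo rate also given in 7.1, power stays at 83.9% or above. The 50% case is extreme: propagation makes up 5.4/12.6 = 43% of the expected placebo events in 7.1.

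**The case against.** The best defence is that the sentence is loose wording for the fixed 3-month period. Much of the plan supports this. The Study Summary makes drug administration last as long as study participation. The exploratory time-to-event analysis in 7.2.1.2 censors subjects lost to follow-up or withdrawing consent, not those who stop drug, and uses treatment period and study period for one window. Section 7.3 plans an on-treatment analysis separately, so the primary analysis was probably not meant to be one. This stands as evidence of intent. A reader might infer that the sponsor chose an on-treatment primary analysis; the documents do not support that. But none of these texts overrides the word *only* in the sentence that governs the primary count, and the safety analysis avoids the drug-use wording.

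A reader might also infer that literal counting costs power through early stops and that the fix recovers it. Step 4 of the working shows the opposite: under the assumptions used, counting all events has lower power at every stopping rate.

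Finally, the scan window might be read as a further contradiction. It is better described as a missing rule. Section 6.2 treats day 90 as a visit label with a tolerance, which suggests that an in-window scan counts. Propagation first seen on day 93 may have occurred at any time since the day-14 scan. The window and the blinded reading are the same in both arms, so this part does not by itself favour either.

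**Conclusion.** The point holds as an error of wording: as written, 7.2.1.2 conflicts with 7.3 and 4.4.3, with the day-90 definition in 3.2 and with its own next paragraph. Followed literally, it drops off-drug events and keeps the subjects. The likely intent is the fixed period, so this is a correction and not a change of design.

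The size is unknown, because the documents give no stopping rate and no share of events found on the last scan. The effect on the apixaban count is probably under one event. That rests on assumed stopping below 16%, halfway on average, with placebo risk afterwards. Where an alternative anticoagulant is started after a bleed, which 4.4.1 leaves to the treating provider, the risk and the loss would probably be smaller. What the correction gains is agreement with intention to treat and freedom from a bias that depends on which arm stops more.

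It should be corrected before anyone sees unblinded results.

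**What to change.** In 7.2.1.2, replace the medication-use sentence with: *All adjudicated primary events from randomization through day 90 will be counted, whether or not study drug was taken or stopped, including thrombus propagation or VTE first found on the protocol Day 90 scan (window to day 97).* Align the day-90 wording in 3.2 and in the net clinical benefit definition with it. Keep any restriction to time on drug for the on-treatment analysis in 7.3. Optionally, add a sensitivity analysis limited to events confirmed by day 90. In the same edit, make the population phrase in 7.2.1.2, which can be read as requiring a dose, match 7.3.

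The cost is a few lines of text and at most one extra analysis; visits, sample size and drug supply do not change. There are two downsides. Counting off-drug events may dilute the effect and lower power slightly (illustratively 78.6% in place of 80.2% at 5% stopping). A few scan-found clots may have begun up to 7 days after day 90, which the sensitivity analysis would show.
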